## 7.2.2 Assessments for Secondary Endpoints

## 7.2.2.1 Prophylactic treatment

The following parameters will be documented:

- Dates and times of study product injections
- Details of dose(s) (in IU) and product batch numbers
- Details of BEs (if any) occurring under prophylactic treatment

Study drug consumption data (FVIII IU/kg per month, per year) per patient and in total (for patients on prophylactic treatment) will be evaluated.

Efficacy Assessment of Prophylactic Treatment

The efficacy of *Human-cl rhFVIII* in prophylactic treatment will be evaluated based on the frequency of spontaneous breakthrough bleeds per months under three times weekly or every other day prophylactic treatment and will be calculated and assessed as excellent, good, moderate or poor:

Excellent:	Less than 0.75 spontaneous BEs permonth
Good:	Between 0.75 and 1 spontaneous BEs per month
Moderate:	Between more than 1 and 1.5 spontaneous BEs per month
Poor:	More than 1.5 spontaneous BEs per month

The time period for prophylactic treatment will comprise the time periods between first prophylactic treatment with *Human-cl rhFVIII* until the administration of the last prophylactic treatment + 2 days or completion visit whatever comes first) minus time periods from start of a surgery until final assessment of the surgery, and minus time period of on demand treatment, if any.

The frequency of treatment will mainly depend on the patient's clinical situation and may vary from every other day to once weekly injections. In cases of inadequate response, *Human-cl rhFVIII* administration frequency or dose adjustments can be considered at Investigator's discretion.

The number of BEs counted for prophylactic treatment efficacy assessment will comprise all BEs starting during the time periods for prophylactic treatment defined above, i.e. BEs occurring between start of surgery until final assessment of the surgery will not be included in the prophylactic treatment assessment.

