- Type of BE (spontaneous, traumatic, post-operative, joint, other)
- Site(s) of BE
- Start date and time of occurrence/of noticing the BE
- Severity of the BE (minor, moderate, major, life threatening)
- Date and time of end of BE*
- Treatment details: dates and times, doses, batch numbers
- BE during inhibitor-free time period

- Frequency of BEs per patient
- Number of infusions needed to treat a BE per patient
- Study drug consumption (FVIII IU/kg BW per infusion, per BE, per month, per year) per patient
- Dose changes: increased and decreased doses of *Human-cl rhFVIII* used to treat individual BEs
For further definition of a dose change, see below (end of this chapter)
- Dose changes: in the doses per infusion and changes in the total dose used to treat subsequent BEs of the same site (e.g. elbow, knee, etc.) in the same patient.
For further definition of a dose change, see below (end of this chapter).
- Details on any concomitant medication used

* If the treatment of a BE at one bleeding site is interrupted for > 48 hours, the events are to be recorded as two separate BEs; if another than the original bleeding site is affected, the events are to be recorded as separate BEs at any time.

Definition of dose change:

A dose change will be considered relevant if the difference in the weight adjusted doses is ≥ 30 IU/kg body weight.

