- **Efficacy: Per Protocol (PP) analysis population**: All subjects in the ITT analysis population who completed the trial without significantly violating the inclusion/exclusion criteria or other aspects of the protocol considered to potentially affect the efficacy results.
Especially the following subjects will be excluded from this population:
 - Subjects who violate the following inclusion criteria:
 - severe haemophilia A (FVIII:C < 1%; historical value as documented in subject records),
 - no previous treatment with FVIII concentrate or other blood products containing FVIII
 - Subjects who fulfil at least one of the following exclusion criteria:
 - other coagulation disorder than haemophilia A
 - severe liver or kidney disease (ALT and AST levels >5 times of upper limit of normal, creatinine >120 $\mu\text{mol/L}$),
 - concomitant treatment with any systemic immunosuppressive drug,
 - Subjects who use concomitant medication that may confound study results, like e.g. alpha-interferon or prednisone
 - Subjects with significant non-compliances with the protocol like for example non-compliance to complete the diary in a proper manner or more than 30% of haemostatic efficacy assessments missing.

- Subjects with dosing or treatment errors like e.g. the use of other FVIII products (except for emergencies) or several *unexplained* and significant deviations from the recommended dose regimen.
- Subjects for whom less than a minimum of inhibitor tests is available*
- Patients with less than 95 days of exposure to *Human-cl rhFVIII*.

*Defined during Data Review Meeting for the interim analysis on April 7, 2016:

if less than 1 inhibitor test is available for any of the following periods:

- baseline, if first result of inhibitor screening after first exposure to the study drug is positive (it cannot be assured that the patient is a PUP),
- between ED2 and ED20,
- between ED21 and ED50.

- Population of subjects on prophylactic treatment schedule (PROPH): All subjects in the ITT population who have at least one prophylactic treatment. Only data under prophylaxis will be used for the analyses.
- Per-protocol population of subjects on prophylactic treatment schedules (PROPH-PP): All subjects in the PP population who have at least 95 EDs of treatment and who have no significant dosing or treatment errors, like e.g. unexplained interruptions of the prophylaxis with *Human-cl rhFVIII*.

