6.1 Summary Tables

All collected efficacy and safety assessments will be presented by means of descriptive statistics. If not detailed otherwise, the parameters listed below will be tabulated according to the different types of data. The number of subjects in the analysis population (N) and the number of subjects contributing to each particular summary (n) will be included in every presentation.

Where appropriate, results will be presented grouped by different subject characteristics, such as bleeding sites or surgery types, as well as in total.

- Binary data (whether or not an event has occurred): counts and proportions
- Count data (the frequency of an event in a set time period): rate (count per unit time)
- Continuous data (measurements on a continuous scale, including quasi-continuous variables): arithmetic mean, standard deviation, median, lower and upper quartile, minimum, maximum
- Scales data (Ordinal and Non-ordinal): absolute and relative frequencies
- Time-to-event data (how long it takes to observe the outcome of interest, e.g. the development of inhibitors to FVIII): time to event or last evaluation (censored data in case subjects are lost to follow-up) and event rate. These parameters might not be tabulated separately, but can be included as an inset into a Kaplan-Meier plot of the product-limit survival function estimates.

In addition this type of data can be shown in life-tables.

Additional descriptive and exploratory statistics, such as geometric means or confidence intervals, are included as appropriate. If not mentioned otherwise, confidence intervals are to be understood as two-sided, 95% confidence intervals.

Please refer to section 13 for a table of tables included in the statistical report.

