- Number of subjects treated prophylactically
- Characteristics and number of prophylactic treatments: Treatment intervals, dosage, changes or interruptions in prophylactic treatments
- Number of injections and exposure days. Injections administered over midnight will only count as exposure day on the day on which the injection had started.
- Amount of *Human-cl rhFVIII* used (per month, per year*, exposure day and injection, and in total)

*projected estimate

- Overall efficacy assessment at the end of the study: Number and rate (per month and per year) of spontaneous BEs in subjects on prophylactic treatment*; in total, as well as broken down to intensity of prophylaxis, timely distance from last study drug administration, dose(s) and characteristics of BE (type, site and severity of BE).

*The rate of BEs will exclude BEs and the time period between start of surgery-related prophylactic treatment and re-start of prophylactic treatment after surgery.

It will also exclude BEs and time periods of “on-demand” treatment, if any.

- In two additional secondary analyses, overall efficacy analysis for prophylactic treatment will be analysed
 - for traumatic BEs
 - for all BEs (spontaneous, traumatic, others (if any)).
- Further analysis on bleeding rates will be performed in patients who developed an inhibitor, but only during their inhibitor-free periods. An inhibitor is regarded as confirmed between its start date, as defined in Chapter 3.4.1, Definition “I4”, and the time when the inhibitor titre decreases again to <0.6 BU for the first time, which has to be confirmed by a subsequent measurement of < 0.6 BU; should the inhibitor titre however not have decreased to < 0.6 BU during the study the period with confirmed inhibitor lasts until the end of the study. Periods of prophylaxis without confirmed inhibitor are regarded as “inhibitor-free”.
- Study drug consumption data for prophylactic treatment (IU FVIII /kg BW per month, per year, exposure days) per subject and in total (for subjects on prophylactic treatment) will be presented descriptively.

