14.2.9	T	Statistics on the dosage of Human-cl rhFVIII (IU/kg) for ITI treatment per month, per year, per exposure day, per injection and in total	ITI
14.2.10	T	ITI: Statistics on changes in treatment schedule	ITI
14.2.11	T	ITI: Frequency table on haemostatic agents used under ITI	ITI
14.2.12	T	ITI: Frequency table on number and percentage of finalized ITI therapy (Number of criteria fulfilled and rate of complete successes)	ITI
14.2.13	T	ITI: Frequency table on number and percentage of individual criteria of success fulfilled	ITI
14.2.14	F	ITI: Kaplan Meier curves on time to complete success (any inhibitor, low titre inhibitor, high titre inhibitor)	ITI
		PROPHYLAXIS	
14.2.15	T	Number of exposure days and number of infusions administered for prophylactic treatment with Human-cl rhFVIII	PROPH, PROPH-PP
14.2.16.1	T	Statistics on the number of exposure days for prophylactic treatment to Human-cl rhFVIII and number of dosages administered	PROPH, PROPH-PP
14.2.16.2	T	Statistics on the number of exposure days for prophylactic treatment to Human-cl rhFVIII and number of dosages administered - restricted to subjects assessed to have received continuous prophylaxis	PROPHcont
14.2.17.1	T	Statistics on the amount of Human-cl rhFVIII (IU) for prophylactic treatment per month, per year, per exposure day, per injection and in total	PROPH, PROPH-PP
14.2.17.2.1	T	Statistics on the dosage of Human-cl rhFVIII (IU/kg) for prophylactic treatment per month, per year, per exposure day, per injection and in total	PROPH, PROPH-PP

14.2.17.2.2	T	Statistics on the amount of Human-cl rhFVIII (IU/kg) for prophylactic treatment per month, per year, per exposure day, per injection and in total - restricted to subjects assessed to have received continuous prophylaxis	PROPHcont
14.2.17.2.3	T	Statistics on the amount of Human-cl rhFVIII (IU/kg) for prophylactic treatment during the inhibitor-free period per month, per year, per exposure day, per injection and in total - restricted to subjects assessed to have received continuous prophylaxis	PROPHcont
14.2.18.1	T	Prophylactic Treatment (dose changes and interruptions of prophylactic treatment)	PROPH, PROPH-PP
14.2.18.2	T	Prophylactic Treatment: Frequency table on haemostatic agents used under prophylactic treatment	PROPH, PROPH-PP
14.2.19.1.1 .1	T	Overall Efficacy Assessment of Prophylactic Treatment (Rate of BEs with 95% confidence interval) – Spontaneous BEs	PROPH, PROPH-PP

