14.2.19.4.1 .1 - 14.2.19.6.7	T	Overall Efficacy Assessment of Prophylactic Treatment... (like 14.2.19.1.1-14.2.19.3.7) – during inhibitor-free periods	PROPH, PROPH-PP
14.2.19.6.8 .1	T	Overall Efficacy Assessment of Prophylactic Treatment (Rate of BEs with 95% confidence interval) - Spontaneous BEs - during time with confirmed inhibitor	PROPH, PROPHPP
14.2.19.6.8 .2	T	Overall Efficacy Assessment of Prophylactic Treatment (Rate of BEs with 95% confidence interval) - Traumatic BEs - during time with confirmed inhibitor	PROPH, PROPHPP
14.2.19.8.3	T	Overall Efficacy Assessment of Prophylactic Treatment (Rate of BEs with 95% confidence interval) - all types of BEs - during time with confirmed inhibitor	PROPH, PROPHPP
14.2.19.7.1		Annualized bleeding rates based on Poisson distribution - Prophylactic treatment	PROPH, PROPHPP
14.2.19.7.2		Annualized bleeding rates based on Poisson distribution - Prophylactic treatment – during inhibitor-free periods	PROPH, PROPHPP
14.2.19.7.3		Annualized bleeding rates based on Poisson distribution - Prophylactic treatment – during inhibitor-free periods – restricted to subjects assessed to have received continuous prophylaxis	PROPHcont

14.2.19.7.4		Annualized bleeding rates based on Poisson distribution – all types of BEs by severity of BE – during inhibitor-free periods – restricted to subjects assessed to have received continuous prophylaxis	PROPHcont
14.2.19.6.8.1	T	Overall Efficacy Assessment of Prophylactic Treatment (Rate of BEs with 95% confidence interval) - Spontaneous BEs - during time with confirmed inhibitor	PROPH, PROPHPP
14.2.20	T	Number of exposure days and infusions administered for on-demand treatment with Human-cl rhFVIII	On-demand
14.2.21	T	Statistics on the number of exposure days for on-demand treatment to Human-cl rhFVIII and infusions administered	On-demand
14.2.22.1	T	Statistics on the amount of Human-cl rhFVIII (IU) for on-demand treatment per month, per year, per exposure days, per injection and in total	On-demand
14.2.22.2	T	Statistics on the dosage of Human-cl rhFVIII (IU/kg) for on-demand treatment per month, per year, per exposure days, per injection and in total	On-demand
14.2.23	T	On-demand: Frequency table on haemostatic agents used under on-demand	On-demand
		BLEEDING EPISODES	
14.2.24.1	T	Number and frequency of bleeding episodes (BEs) per subject (overall)	ITT, PP
14.2.24.2	T	Number and frequency of bleeding episodes (BEs) per subject - during inhibitor-free periods	ITT, PP

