16.2.6.1	L	Number of bleeding episodes, rate per month, rate per year, overall efficacy of prophylactic treatment, characteristics of BE (3 subtables for spontaneous, traumatic and all BEs + 3 subtables for prophylactic treatment in inhibitor-free period)	ITT
16.2.6.3	L	Bleeding episodes during study (including BEs in BLEED population and BEs not in BLEED population)	All BEs
16.2.6.4	L	Bleeding episodes, doses and changes in dose per infusion for each bleeding episode during study	BLEED, BLEED-PP
16.2.6.5	L	Bleeding episodes by site of BE, efficacy assessments, doses per BE and per infusion by site of BE	BLEED, BLEED-PP
16.2.6.6	L	Other per subject data on BEs in BLEED population	All
16.2.6.9.1.1	L	Surgeries: Description and outcome of surgical procedures	SURG, SURG-PP
16.2.6.9.1.2	L	Description and outcome of surgical procedures – Criteria for major severity, Hospitalization	
16.2.6.9.2	L	Surgeries: Description of wound hematoma yes/no and whether it needed surgical evacuation yes/no	SURG, SURG-PP
16.2.6.9.3	L	Surgeries: Description and assignment to SURG/SURG-PP populations including reasons for exclusion	SURG, SURG-PP
16.2.6.9.4	L	Surgeries: Blood loss (planned and actual), duration of surgery (planned and actual)	SURG, SURG-PP
16.2.6.10	L	Medical resource use data not covered in other listings: CVAD type, CVAD use, complications and management of the complications, hospitalization (including ward type) and duration	All
16.2.6.11	L	Additional health economic evaluation	All
16.2.7.1	L	Treatment-Emergent adverse Events (inc. indicator for phase of study: prophylactic, surgery, on-demand, ITI)	All
16.2.7.2	L	Possibly/probably related treatment-emergent adverse events (according to investigator and/or sponsor)	All
16.2.7.3	L	Non-treatment emergent adverse events	All
16.2.8.1	L	Laboratory assessments (Haematology, Clinical chemistry) (2 sub-listings: hematology, clinical chemistry)	All
16.2.8.2	L	FVIII:C, Inhibitors at baseline and during study	All
16.2.8.3	L	Confirmed occurrence of inhibitor, time from ED1 to confirmed inhibitor occurrence and number of EDs before inhibitor development, if any	All
16.2.8.4	L	Assessment of success in patients with inhibitors/ ITI therapy	ITI
16.2.8.5	L	Epitope mapping (in case of inhibitor development)	ITI
16.2.8.6	L	Vital signs	SAF
16.2.8.7.1	L	Physical examination	All
16.2.8.7.2	L	Abnormal findings of physical examination	SAF
16.2.9.1	L	Additional comments provided in the CRF	All

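### Tables 14.2.19.7.1 to 14.2.19.7.4 rest annualised bleeding rates on a Poisson distribution; any plain Poisson interval reported there would be too narrow if patients' rates differ

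*SAP*

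**What the plan says.** The Poisson basis appears only in the table list of SAP section 13. Table 14.2.19.7.1 is titled "Annualized bleeding rates based on Poisson distribution - Prophylactic treatment". Tables 14.2.19.7.2 and 14.2.19.7.3 restrict this to inhibitor-free periods, and 14.2.19.7.3 further to continuous prophylaxis. Table 14.2.19.7.4 gives Poisson-based rates for all bleed types by severity, with both restrictions. None of the four titles mentions an interval. The neighbouring tables do: "Overall Efficacy Assessment of Prophylactic Treatment (Rate of BEs with 95% confidence interval", with no method stated.

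The body of the SAP does not mention Poisson. Section 6.1 says "Count data (the frequency of an event in a set time period): rate (count per unit time", and allows confidence intervals where appropriate (two-sided, 95% unless stated otherwise). Section 9.2 asks for the number and rate of spontaneous bleeds, "in total, as well as broken down to intensity of prophylaxis" and by other characteristics. Section 6.4.1 marks covariate adjustment as not applicable, and section 6.4.4 plans no centre-effect analysis. Neither document gives a dispersion parameter, random effect or robust variance for bleeding rates.

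On who and what is counted:

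- The PROPH population (SAP 5.1) is "All subjects in the ITT population who have at least one prophylactic treatment".
- Protocol 7.2.2.1 says that treatment frequency "may vary from every other day to once weekly injections".
- SAP 3.4.2 says of bleeds that "if another than the original bleeding site is affected, the events are to be recorded as separate BEs at any time".

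**The concern.** Dividing bleeds by time needs no distribution, so naming Poisson matters mainly for a standard error or interval. A plain Poisson interval assumes that all patients share one rate and that bleeds occur independently. Several terms of the plan work against this:

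- Injection frequency spans every other day to once weekly, and the recommended dose spans 20-50 IU/kg (Protocol 5.4).
- PROPH has no minimum duration and no required regimen.
- Simultaneous bleeds at two sites are two events in one patient, so events cluster.
- Table 14.2.19.7.1 is not restricted by inhibitor status, so it includes any inhibitor time still on prophylaxis.

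Tables 14.2.19.7.2 to 14.2.19.7.4 remove inhibitor time. The last two also require at least 169 days of prophylaxis and exclude mixed regimens, apart from patients treated on demand only once before switching. Heterogeneity should be smaller there, but differences in dose and frequency and the clustering of bleeds remain.

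At stake is the stated precision of the annualised rate. With no formal test planned, an interval is what a reader would use to judge how firmly that rate is known.

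**Working it through.** The documents give no expected bleeding rate, dispersion or standard error, so there is no figure of the plan's own to reproduce. The rates, dispersions and patient numbers below are assumptions.

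**Formula.** Let patient rates follow a gamma distribution with mean r per year and shape k, and let each patient contribute T years. A patient's count then has variance rT + (rT)²/k, the negative binomial form; smaller k means larger differences. Over n patients:

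- true variance of the total = n·rT·(1 + rT/k)
- plain Poisson variance = n·rT
- width factor needed = sqrt(1 + rT/k)
- coverage of a nominal 95% Poisson interval = 2Φ(1.96/factor) − 1

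The number of patients cancels, so enrolling more does not cure the shortfall.

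**Illustration, r = 3 and T = 1.**

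| k | width factor | coverage |
|---|---|---|
| no heterogeneity | 1.00 | 95% |
| 7 | sqrt(1 + 3/7) = 1.20 | 90% |
| 4 | sqrt(1 + 3/4) = 1.32 | 86% |
| 2 | sqrt(1 + 3/2) = 1.58 | 78.5% |
| 1 | sqrt(1 + 3) = 2.00 | 67% |
| 0.5 | sqrt(1 + 6) = 2.65 | 54% |

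On the rate scale, suppose 300 bleeds in 100 patient-years, a rate of 3.0. The plain Poisson log-scale interval is 3·exp(±1.96/sqrt(300)) = 2.68 to 3.36. Multiplying the log-scale standard error by the factor gives 2.51 to 3.59 at k = 2 and 2.22 to 4.05 at k = 0.5.

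**Unequal time, and whether the remedy works.** Simulation used 6000 runs per setting, 90 patients and 3 bleeds per year. Prophylaxis time was uniform from 0.46 years (169/365.25, the continuous-prophylaxis minimum in SAP 5.1) to 1.92 years (100 exposure days once weekly = 700 days; 700/365.25). It compared the exact Poisson interval with a patient-level sandwich interval on the log scale.

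| k | Poisson coverage | robust coverage | width ratio |
|---|---|---|---|
| no heterogeneity | 95.6% | 95.1% | 1.00 |
| 7 | 88.6% | 94.8% | 1.25 |
| 2 | 74.6% | 94.7% | 1.71 |
| 0.5 | 48.9% | 94.0% | 2.91 |

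The 0.46-year floor does not apply to PROPH. Lowering it to 0.05 years gives similar Poisson coverage: 89.1%, 76.2% and 51.0% for k = 7, 2 and 0.5.

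**Rare bleeds.** With the 0.46 to 1.92 year range and k = 0.5, Poisson coverage is 93.6% at 0.1 bleeds per year and 96.4% at 0.05 (among runs with at least one bleed). Sparse cells, such as the severe categories of Table 14.2.19.7.4 might be, would lose little.

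**The case against.** The strongest reply is that these four titles promise no interval, while their neighbours do. If only rates are tabulated, nothing is wrong. A Poisson basis also does not exclude scaled or robust variance, so silence should not be read as a plain Poisson interval. This stands, and the point is therefore conditional. It does not remove the point: a distribution is named, SAP 6.1 provides for intervals, and SAP section 1 undertakes to describe the analyses fully.

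Second, between-patient spread is already shown. Tables 14.2.24.1-2 and 14.2.38.1-2 summarise bleeds per subject. Listing 16.2.6.1 gives "Number of bleeding episodes, rate per month, rate per year, overall efficacy of prophylactic treatment". Rates are also broken down by intensity of prophylaxis, site, severity and inhibitor status. This too stands, but these outputs describe the spread without widening a Poisson interval.

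Third, a reader might infer that Table 14.2.19.7.1 pools all inhibitor time. The documents do not support that. SAP 9.3 treats immune tolerance induction as a treatment type separate from prophylaxis, so only inhibitor time still on prophylaxis would enter, and separate tables show bleeding rates for time with a confirmed inhibitor.

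Fourth, the size depends wholly on assumed values, and the lowest coverage comes from the most extreme k. That is correct.

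**Conclusion.** The point holds in conditional form, at low priority. The plan names a Poisson basis for four annualised-rate tables and states no allowance for differences between patients. If a plain Poisson standard error or 95% interval is reported there, it will overstate precision to the extent that rates differ, and the plan's own terms make some difference likely. The size is not determinable from the documents. The range of about 90% to 54% coverage rests on 3 bleeds per year, one year each and k from 7 to 0.5.

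A reader might go further and infer that the trial's bleeding-rate intervals in general are too narrow. The documents do not support that: the neighbouring rate tables give no method and may rest on per-patient rates. Nor is the estimated rate wrong. Total bleeds over total time, the excellent-to-poor grading and the per-subject summaries are unaffected. SAP 6.4 makes the analysis exploratory, so no test decision depends on it.

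**What to change.** Add a short paragraph to the SAP for Tables 14.2.19.7.1 to 14.2.19.7.4:

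- Estimate the rate as total bleeds over total prophylaxis time.
- Take any 95% confidence interval from a Poisson model with log(prophylaxis time) as offset and patient-level robust (sandwich) variance, with one record per patient and cell. A negative binomial model with the same offset is an acceptable alternative.
- Report the dispersion estimate (Pearson chi-square over n − 1).
- In a cell with no bleeds, give the exact Poisson upper limit and label it as such, because it still assumes a common rate.

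The cost is one paragraph, one model option and slightly more programming. Intervals become wider where patients differ and barely change where they do not. In small, strongly heterogeneous groups the robust interval is itself slightly short: simulated coverage was 93.0% with 50 patients and k = 0.5.

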# 9.2.4 Safety Analysis Plan

All AEs occurring after initiation of study treatments (including events likely to be related to the underlying disease, or a concomitant illness or medication or clinical significant abnormalities in laboratory parameters or vital signs) will be displayed in summary tables, listings and figures.

Incidences of AEs will be given as numbers and percentages of patients and infusions with:

- Any AE.
- Any serious AE.
- Any AE probably or possibly related to the trial drug.
- Any AE that begins within 24 hours of the end of an infusion.
- Any severe AE.
- Any withdrawal due to AE.
- Any AE by MedDRA preferred term.
- Any AE by MedDRA System Organ Class (SOC).

Summary tables for AEs will be given by SOC and preferred term. Additionally, AEs will be summarised by severity and relationship to study treatment. These summary tables will feature total counts and counts by age group, sex, prior EDs to *Human-cl rhFVIII* and total amount of *Human-cl rhFVIII* used prior to the AE to evaluate the need of further investigation of any apparent pattern or trend in AE rates.

The MedDRA coded terms and the corresponding original (verbatim) terms used by the Investigator will be listed.

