Summary tables for AEs will be given by SOC and preferred term. Additionally, AEs will be summarized by severity and relationship to study treatment. These summary tables will feature total counts and counts, prior exposure days to *Human-cl rhFVIII* and total amount of *Human-cl rhFVIII* used prior to the AE to evaluate the need of further investigation of any apparent pattern or trend in AE rates.

The MedDRA coded terms and the corresponding original terms used by the investigator will be listed.

All adverse events for each subject will be listed in Appendix 16 of the CSR, featuring the following data:

- Subject identifier and characteristics (age, weight)
- The adverse event (preferred term, reported term)
- Onset, date of resolution and duration of the adverse event
- Severity (mild, moderate, severe)
- Seriousness (serious/non-serious)
- Action taken - General (none, drug therapy (other than IMP) started, tests performed, other (to be specified)) and on study drug (none, product withdrawn, dose reduced, dose increased)
- Outcome (recovered, recovering, not recovered, recovered with sequelae, fatal, unknown)
- Causality assessment (probable, possible, unlikely, not related)
- Study treatment at time of event or most recent study treatment taken, including dose and batch number
- Previous exposure to *Human-cl rhFVIII* (exposure days and total amount used)

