14.3.1.2	T	Summary of treatment-emergent adverse events (number of subjects/infusions with any AE, SAE, Severe AE or possibly or probably related AE, AEs that begin within 24 hours of end of infusion)	SAF, Safety-INF
14.3.1.3	T	Treatment-emergent adverse events by preferred term by subject (descending frequency)	SAF
14.3.1.4	T	Treatment-emergent adverse events by preferred term by infusion (descending frequency)	Safety-INF
14.3.1.5	T	Treatment-emergent adverse events by system organ class and preferred term	SAF, Safety-INF
14.3.1.6.1	T	Treatment-emergent possibly/probably related (acc. to investigator) adverse events by system organ class and preferred term	SAF, Safety-INF
14.3.1.6.2	T	Treatment-emergent possibly/probably related (acc. to sponsor) adverse events by system organ class and preferred term	SAF, Safety-INF
14.3.1.7	T	Treatment-emergent adverse events temporally related (within 24 hours after end of infusion) by system organ class and preferred term	SAF, Safety-INF
14.3.1.8	T	Severity of treatment-emergent adverse events by system organ class and preferred term	SAF
14.3.1.9	T	Severity of treatment-emergent adverse events by system organ class and preferred term	Safety-INF
		Sub-group analyses	
14.3.1.12	T	Summary of treatment-emergent adverse events – by total amount of Human-cl rhFVIII before AEs	SAF, Safety-INF
14.3.1.13	T	Treatment-emergent adverse events by system organ class and preferred term – by total amount of Human-cl rhFVIII before AEs	SAF, Safety-INF
14.3.1.14	T	Summary of treatment-emergent adverse events – by number of EDs with Human-cl rhFVIII before AEs	SAF, Safety-INF
14.3.1.15	T	Treatment-emergent adverse events by system organ class and preferred term – by number of EDs with Human-cl rhFVIII before AE0	ITI
14.3.1.16	T	Summary of adverse events – during ITI	ITI, Safety-INF
14.3.1.17	T	Treatment-emergent adverse events by system organ class and preferred term – during ITI	ITI
14.3.1.18	T	Summary of adverse events – by prophylactic treatment class (on prophylaxis vs. on on-demand)	SAF, Safety-INF
14.3.1.19	T	Treatment-emergent adverse events by system organ class and preferred term – by prophylactic treatment class (on prophylaxis vs. on on-demand)	SAF
14.3.1.20	T	Summary of adverse events – during and after surgical interventions (up to end of post-surgical treatment)	SAF, Safety-INF

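### SAP Table 14.3.1.15, the only adverse event table crossing term with prior exposure days, is assigned to ITI patients only, against SAP 11.1 and Protocol 9.2.4

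*SAP*

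**What the plan says.** SAP section 13 lists the output that will be generated. Its safety subgroup block pairs a summary table with a by-term table for each way of splitting adverse events.

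- Tables 14.3.1.12 (summary) and 14.3.1.13 (system organ class and preferred term) are split "by total amount of Human-cl rhFVIII before AEs". Both are assigned to SAF and Safety-INF.
- Table 14.3.1.14 (summary) is split "by number of EDs with Human-cl rhFVIII before AEs". It is assigned to SAF and Safety-INF.
- Table 14.3.1.15 (system organ class and preferred term) is split "by number of EDs with Human-cl rhFVIII before AE0". It is assigned to ITI only.
- Tables 14.3.1.16 and 14.3.1.17 are the ITI safety tables, and their titles say that they cover events during ITI.

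SAP 11.1 says of the adverse event tables: "Summary tables for AEs will be given by SOC and preferred term". It goes on: "These summary tables will feature total counts and counts, prior exposure days to" the study product, and also the total amount "used prior to the AE to evaluate the need of further investigation of any apparent pattern or trend in AE rates". Protocol 9.2.4 makes the same commitment, with counts by "prior EDs to *Human-cl rhFVIII* and total amount of *Human-cl rhFVIII* used prior to the AE". Neither section confines these tables to patients on ITI.

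**The concern.** The population of Table 14.3.1.15 does not match its title, its sister tables or the text that it implements. SAP 5.1 defines the safety population as everyone who received at least one dose, whereas patients with ITI treatment are a subpopulation of the ITT set. Under Protocol 5.4, ITI is offered only after a clinically significant, non-transient inhibitor. A programmer who follows section 13 literally would therefore build the table on a selected minority.

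At stake is the planned view of which adverse event terms occur at which level of prior exposure in all treated patients. SAP 11.1 gives the purpose of the split as deciding whether an apparent pattern or trend needs further investigation. A table limited to ITI patients cannot serve that purpose for the others. The ITI patients differ by definition: they have already developed an inhibitor and receive a different regimen.

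**Working it through.** There is no sample size, power or other calculated figure to reproduce. The check is a comparison of table entries, followed by simple arithmetic on coverage.

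**Step 1: does another table fill the gap?** All adverse event tables in SAP section 13 were compared on three features.

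| Table | By term | Split by prior EDs | Population |
|---|---|---|---|
| 14.3.1.5 | yes | no | SAF, Safety-INF |
| 14.3.1.6.1, 14.3.1.6.2 (related) | yes | no | SAF, Safety-INF |
| 14.3.1.7 (within 24 hours of infusion) | yes | no | SAF, Safety-INF |
| 14.3.1.13 | yes | no, by total amount | SAF, Safety-INF |
| 14.3.1.14 | no, summary only | yes | SAF, Safety-INF |
| 14.3.1.15 | yes | yes | ITI |
| 14.3.1.17 | yes | no | ITI |
| 14.3.1.19 (prophylaxis or on-demand) | yes | no | SAF |

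The remaining adverse event tables do not cross term with prior exposure days either. Table 14.3.1.15 is the only one that does.

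**Step 2: is ITI the intended population?** Three features suggest a slip. The title has no ITI wording, whereas the titles of 14.3.1.16 and 14.3.1.17 do. The direct counterpart, 14.3.1.13, covers all treated patients. The row has a second visible error, AE0 where the neighbouring titles have AEs. The entry could have been carried over from the two ITI rows directly below.

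**Step 3: how many patients would be missing?**

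Inputs:
- Planned patients: N = 100 (SAP 4.2).
- Inhibitor incidence, first value: up to about 30% (Protocol 1.1).
- Inhibitor incidence, second value: 44.5%, which SAP section 2 cites for recombinant FVIII from hamster cell lines in previously untreated and minimally treated patients.
- Share of inhibitor patients who start ITI: not given. It is assumed to be 100%, which makes the table as full as possible.

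Formula: missing = N × (1 − incidence × share starting ITI).

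- At 30%: 100 × (1 − 0.30 × 1) = 70 missing, 30 covered.
- At 44.5%: 100 × (1 − 0.445 × 1) = 55.5, so about 55 missing and about 45 covered.

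A share below 100%, because some inhibitors are transient or some families decline ITI, raises the number missing at either incidence.

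**Step 4: can Table 14.3.1.13 stand in?** Only in part. Total amount rises with exposure days but also depends on body weight and on dose per day. Protocol 5.4 recommends 20-50 IU/kg for a prophylactic dose and 100-150 IU/kg every 12 hours for high responders on ITI. Per day of treatment, the extremes are 20 IU/kg and 2 × 150 = 300 IU/kg, a ratio of 300 / 20 = 15. In a table that pools both groups, the same amount can mean very different numbers of exposure days.

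**The case against.** The strongest reply is that this is a clerical slip in one cell and costs little. Nobody appears to have chosen the restriction, and the body text of the SAP is right. The affected patients are well covered elsewhere. Their events appear by term in 14.3.1.5, by term and cumulative amount in 14.3.1.13, and by exposure days in summary form in 14.3.1.14. Related and infusion-associated events appear by term in 14.3.1.6.1, 14.3.1.6.2 and 14.3.1.7. SAP 11.1 also has the per-subject adverse event listing show prior exposure days and amount for each event, so with about 100 patients the missing view could be rebuilt by hand. Under Protocol 8.6 an independent committee reviews inhibitor and safety data at least yearly.

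Most of this stands, and it limits the point to one cross-tabulation. It does not remove the inconsistency, because section 13 states what will be produced and no other listed table has this content.

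A reader might infer that early-exposure reactions in patients without ITI would go unseen. The documents do not support that. Besides the coverage just listed, neither document says that adverse events in general concentrate in the first exposure days. Protocol 1.1 makes a statement of that kind only for inhibitors, whose timing is analysed separately in the ITT population (Table 14.2.2.2, the Kaplan-Meier output and the life-tables in steps of 5 EDs). Nor do the documents set exposure-day bands for the adverse event tables; the classes in SAP 5.1 are for inhibitor incidence. Even the corrected table is therefore not shown to isolate the earliest exposures.

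**Conclusion.** The inconsistency is real and minor. As listed, Table 14.3.1.15 would omit every patient without ITI, contrary to SAP 11.1 and Protocol 9.2.4, and no other listed table replaces it. The primary endpoint and the collection of adverse event data are not affected.

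The size, about 55 to 70 of 100 patients, is an assumption and not a planned figure. It rests on the two incidences quoted in the documents and on every inhibitor patient starting ITI. A reader might take 70 as a minimum because Protocol 1.1 speaks of up to about 30%. That is not a bound, since the SAP itself cites 44.5% for other recombinant products. The denominator may also exceed 100, because Protocol 4.3.2 replaces patients withdrawn with fewer than 50 EDs, while anyone who received a dose stays in the safety population. At either incidence, most treated patients are absent from the table.

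That SAP 11.1 and Protocol 9.2.4 mean all treated patients is a reading of their text. Both sections open with all adverse events after the start of treatment, but the sentences on prior exposure name no population.

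**What to change.** In SAP section 13, change the population of Table 14.3.1.15 from ITI to SAF and Safety-INF, and correct AE0 to AEs in its title. SAF is the essential part; Safety-INF is added to match 14.3.1.13. If an ITI-only version is wanted, list it as a separate table with ITI in its title, as for 14.3.1.16 and 14.3.1.17.

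The cost is one population cell and one character in the table list. No new data are needed, because prior exposure days are already derived for the adverse event listing and for Table 14.3.1.14. If the output has already been programmed, the table should be rerun on the safety population.
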